12.4.2 Analysis Plan

Fisher's exact tests will be used to determine significance of differences in lymphedema rates between LYMPHA and the lymphadenectomy alone control arm, and significance of differences in lymphedema rates between LYMPHA and the lymphadenectomy with STR control arm. If treatment arms differ significantly at baseline in demographics (for e.g. age), lymphedema status at the end of treatment will be compared between treatment groups via a logistic regression, using the necessary covariates. Depending on the attrition rate, we may also use mixed effects logistic regression models to determine whether the treatment arms significantly differ in the binary endpoint (lymphedema status). Mixed models automatically handle missing data, producing unbiased estimates as long as observations are missing at random. This allows the use of all available data from all subjects, thereby minimizing the effects of loss to follow-up.

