2.4 Study Design

We propose a randomized clinical trial to determine the efficacy of the LYMPHA procedure in breast cancer patients undergoing axillary lymphadenectomy.

Up to 100 subjects will be enrolled in the trial; they will undergo either lymphadenectomy, lymphadenectomy with soft tissue reinforcement (STR) or lymphadenectomy with LYMPHA. Subjects must meet all additional defined inclusion and exclusion criteria.

Please note that soft tissue reinforcement is common practice and used as the standard of care in some lymphedema centers. The addition of this group is important because it allows a comparison of LYMPHA to a currently commonly practiced alternative and the ability to assess for superiority of the LYMPHA procedure. In short, at Stanford, we perform soft tissue reinforcement with collagen scaffolding commonly and would like to start including these patients in our prospective analysis/study.

All patients that are enrolled will be randomized into one of three groups: Group A (surgical control group 1) – the patients will undergo lymphadenectomy alone with simple wound closure, Group B (surgical control group 2) – the patients will undergo lymphadenectomy with soft tissue reinforcement using a collagen scaffold, or Group C (treatment group) - the patients will undergo lymphadenectomy and LYMPHA at the time of wound closure as an adjunct to lymphadenectomy procedure.

Randomization will occur after it has been determined that patients are eligible for the trial intraoperatively. Patients are deemed eligible for the trial intraoperatively if ALND is performed and there are available lymphatics to bypass.

The study will be double blind and randomized. Each patient will be randomized to either the treatment or control group 1 or 2 and will be blinded to their group. While the surgeons will not be blinded, all personnel who track outcomes in clinic will be blinded. The primary outcomes that the protocol is designed to evaluate include efficacy, safety, and impact on the quality of life.

The study was started with 2-arm design (Group A and Group C). A preliminary assessment to the trial effects will be conducted using the current collected data. After the revised protocol is approved, the study will recruit subjects in the new 3-arm phase: 90 subjects (30 subjects per arm in the three groups (Groups A, B, C)

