12. STATISTICAL CONSIDERATIONS

12.1 Statistical Design

The objectives of the study are to assess the efficacy of the LYMPHA procedure when compared to the results of wound closure alone and wound closure with soft tissue reinforcement in similar clinical cohorts. We plan to enroll a total of 100 patients in this randomized parallel clinical trial.

The hypothesis to be tested is that adjunctive surgical use of LYMPHA with an axillary lymphadenectomy will produce a superior effect in terms of lymphedema prevention when compared to the effect of an axillary lymphadenectomy alone and an axillary Axillary lymphadenectomy with STR. The primary endpoint, incidence of lymphedema at month 12, will be compared between LYMPHA and the control, axillary lymphadenectomy alone arm using a significance level of 5%.

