12.1.1 Randomization

Since this study was started with two groups (A and C), and randomized 13 patients to the control group A and 14 patients to the treatment group C. However, 7 of the 14 patients that were randomized to treatment group C did not receive LYMPHA surgery, were considered screen fails, Therefore in the preliminary assessment, 27 patients will be used in intent-to-treat (ITT) analysis, however, 7 screen fails will not be counted in the per protocol (PP) analysis. In the new 3-arm phase, the randomization procedures will happen during ALND surgery time. and 90 subjects will be allocated in a 1:1:1 randomization into three groups. The clinic staff obtaining measurements will be blinded to the treatment group.

A Randomized Clinical Trial of the LYMPHA procedure for the Prevention of Lymphedema after Axillary Lymphadenectomy

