12.6.2 Sample size justification

The risk of lymphedema development is considered to be 30% in the surgical control group (group A), and studies have shown it is to be reduced to 4% when LYMPHA is applied during an axillary lymphadenectomy [12, 30]. With N=40 subjects (20 subjects per arm A and C) in the first stage, the power to stop after the first stage is 56%. Finally, with additional N=40 subjects (20 subjects per arm A and C) in the second stage, the overall power to stop at either the first or the second stage is 88%.

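### Fisher's exact test for the primary comparison is valid but conservative near 30 per arm; Boschloo's exact test would add roughly 1 to 13 points of power within the same 5% level, provided C vs B is no longer an unadjusted primary test

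*Protocol*

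**What the plan says.** Section 12.4.2 fixes the primary test: Fisher's "exact tests will be used to determine significance of differences in lymphedema rates", applied to LYMPHA (Group C) against lymphadenectomy alone (Group A) and to LYMPHA against soft tissue reinforcement (Group B). Section 12.1 attaches the level to the first of these only, comparing LYMPHA with the "axillary lymphadenectomy alone arm using a significance level of 5" per cent. It does not say whether the test is one- or two-sided.

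The size of the three-arm phase is given in 2.4 ("90 subjects (30 subjects per arm in the three groups (Groups A, B, C") and again in 12.1.1 ("90 subjects will be allocated in a 1:1:1 randomization into three groups").

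The planning rates are in 12.6.2: "The risk of lymphedema development is considered to be 30% in the surgical control group (group A"), "reduced to 4% when LYMPHA is applied during an axillary lymphadenectomy". The only power figures are also there, for a two-stage A vs C design. With 20 per arm, "the power to stop after the first stage is 56" per cent; with 40 per arm in total, the overall figure is 88%. No power is stated for Fisher's test or for 30 per arm.

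**The concern.** Fisher's test conditions on the total number of events. With small arms and few events the conditional distribution has few attainable p-values, so the true type I error can fall well below the nominal level. The unused part of the level is lost power.

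Here the arm sizes are set by the design, so an unconditional exact test is also valid. Boschloo's test uses Fisher's p-value as its statistic and raises the cut-off as far as the 5% limit on the maximum type I error allows. It therefore rejects every table that Fisher's test rejects, and usually some more.

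At stake are borderline results in the range that the protocol plans for. With 30 per arm, 5 vs 0 events and 7 vs 1 events (A vs C) give Fisher p-values of 0.0522 and 0.0523. Both would be reported as not significant, although an exact test at the same 5% level would reject.

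**Working it through.** **Inputs.** Rates 30% (A) and 4% (C), from 12.6.2; 30 per arm, from 2.4 and 12.1.1; level 5%, from 12.1. Assumptions, because the protocol gives no figure: two-sided test, a single analysis, no loss unless shown.

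**The protocol's own figure.** 12.6.2 names no stopping boundary. A two-look normal approximation with unpooled variance and a two-sided 5% Pocock boundary (2.178 at each look) reproduces it:

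- Variance term: 0.30×0.70 + 0.04×0.96 = 0.2484.
- 20 per arm: SE = √(0.2484/20) = 0.1114; z = 0.26/0.1114 = 2.333; power = Φ(2.333 − 2.178) = 56.2% (stated 56%).
- 40 per arm: SE = √(0.2484/40) = 0.0788; z = 3.299. The chance of crossing at either look, with correlation √(20/40), is 88.2% (stated 88%).

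The 88% therefore belongs to 40 per arm and a normal approximation.

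**Method at 30 vs 30.** All 31 × 31 tables were enumerated.

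- Power = sum over the rejection region of Bin(a; 30, 0.30) × Bin(c; 30, 0.04).
- Size = maximum over a common rate p (grid of 999 values) of the same sum with both rates equal to p.
- Boschloo's region = tables with Fisher p ≤ k, where k is the largest cut-off with size at most 5%. This gives k = 0.0692.

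| 30 vs 30 | Fisher | Boschloo |
|---|---|---|
| Maximum size | 2.74% | 4.69% |
| Power, 30% vs 4% | 68.9% | 76.0% |
| Power, 30% vs 10.3% | 35.8% | 41.1% |

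**Where the gain comes from.** For 0, 1, 2 and 3 events in C, Fisher's test needs at least 6, 8, 9 and 11 events in A; Boschloo's needs 5, 7, 9 and 10. The added tables contribute, at 30% vs 4%:

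- 5 vs 0: 0.0464 × 0.2939 = 1.4 points
- 7 vs 1: 0.1219 × 0.3673 = 4.5 points
- 10 vs 3: 0.1416 × 0.0863 = 1.2 points

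Together these give 7.1 points. Fisher's test would need about 33 per arm (75.8%) to match.

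**Dependence on the final arm sizes** (A/C, 30% vs 4%):

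| A/C | Fisher max. size | Fisher power | Boschloo power | Gain (points) |
|---|---|---|---|---|
| 30/30 | 2.7% | 68.9% | 76.0% | 7.1 |
| 29/30 | 3.6% | 76.9% | 82.5% | 5.6 |
| 30/29 | 3.6% | 69.7% | 76.8% | 7.1 |
| 29/31 | 3.9% | 80.4% | 81.8% | 1.4 |
| 28/30 | 3.7% | 78.9% | 80.2% | 1.3 |
| 29/29 | 2.5% | 66.3% | 77.6% | 11.4 |
| 28/28 | 2.8% | 63.5% | 75.5% | 12.0 |
| 27/27 | 2.6% | 60.5% | 73.2% | 12.7 |
| 43/44 (two-arm patients pooled: 30+13, 30+14) | 3.9% | 93.0% | 93.7% | 0.8 |

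Fisher's power does not rise smoothly with sample size, because its attainable levels jump from one split to the next.

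**Two comparisons sharing arm C.** With 30 per arm and a common rate q in all arms, let r(c) be the chance that a control arm yields a rejection when C has c events. The chance of at least one false rejection is Σ Bin(c; 30, q) × [1 − (1 − r(c))²]. Its maximum is about 5.1% with two unadjusted Fisher tests and about 8.5% with two unadjusted Boschloo tests.

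**The case against.** Fisher's test is valid, familiar and keeps the level, so nothing in 12.1 or 12.4.2 is false on this point. That stands: the remark concerns efficiency only.

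Four stronger readings are tempting, and none is supported.

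- **Fisher's test always wastes half the level and costs 7 points.** That describes exactly 30 vs 30. At 29/30 or 29/31 its maximum size is 3.6 to 3.9%, and the gain can be as small as about 1 point. Randomization during surgery and loss before month 12 make exactly equal evaluable arms uncertain.
- **The change costs nothing.** It needs no extra patients. But 12.4 and 12.4.2 list two efficacy comparisons, and Fisher's conservatism is what holds their joint error near 5%. With Boschloo's test for both, unadjusted, it rises to about 8.5%, so a restriction on C vs B is part of the change. That restriction agrees with 10.1 and 12.1, which make C vs A the primary comparison, and with 10.2.1 and 12.5, which list pairwise comparisons as secondary.
- **The change restores the planned power.** It does not: 76.0% at 30 per arm remains below 88%, and the sample-size statement needs its own correction.
- **The analysis set is certainly 30 vs 30.** Sections 12.1.1 and 12.2 tie the 27 two-arm patients to a preliminary assessment, but 3.4 and 12.4.1 are worded more broadly. Pooling is not clearly stated; if it were done, the gain would fall below 1 point.

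Sidedness is also unstated. A one-sided 2.5% test gives the same powers at 30 vs 30; a one-sided 5% test gives 79.6% and 87.7%.

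**Conclusion.** The point holds as an optional improvement. For C vs A, with a two-sided 5% level, one look, 30 vs 30 evaluable patients and rates of 30% vs 4%, Boschloo's test raises power from 68.9% to 76.0% with a maximum type I error of 4.7%. At the other splits near 30 per arm shown above, the gain runs from about 1 to about 13 points. Since Boschloo's region contains Fisher's, power is never lower at any split. A stage-wise boundary or an adjustment for a second comparison would lower the level per test, and the powers of both tests would fall.

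**What to change.** Before any three-arm outcome data are seen, amend 12.4.2 to:

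- name Boschloo's unconditional exact test, two-sided 5%, for the single primary comparison C vs A, matching 10.1 and 12.1;
- keep Fisher's exact test for that comparison as a sensitivity analysis;
- make C vs B secondary, matching 10.2.1 and 12.5, or test it only after C vs A succeeds, and bring 12.4 into line.

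The cost is a few sentences and standard software, with no added patients or measurements. The downsides are a test that readers know less well, and that C vs B can no longer serve as a second unadjusted primary comparison.

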2. Limb volume. The volume of the at-risk and the contralateral arm of each subject will be measured through serial quantitation of the limb circumference at 4 cm intervals along its long axis. The procedure is performed with gauged tape to ensure a uniform stretching force. Using these measurements, the volume of the limb is calculated with the truncated cone approximation [20]. Pre- and post-treatment measurements for each subject will be performed by the same operator who, in all cases, will be blinded to the patients' treatment status and to pre-treatment measurement values at the time of the post-treatment assessment. The measured limb volumes at each evaluation will be utilized to generate two data points: the volume V_r of at-risk arm and the volume V_c of contralateral arm. These data will be used to determine a relative excess volume $E = ((V_r - V_c)/V_c) \cdot 100\%$ for each patient at the time of measurement [32]. Change in the relative

A Randomized Clinical Trial of the LYMPHA procedure for the Prevention of Lymphedema after Axillary Lymphadenectomy

excess volume will be determined at month 12 as $(E_{12}/E_0 - 1) \cdot 100\%$, where E_0 is the relative excess volume at baseline ($t=0$) and E_{12} is the relative excess volume at 12 months ($t=12$).

3. Skin thickness measurements: These will be performed with a Lange skinfold caliper (Beta Technology, Santa Cruz, CA). For each subject, at each assessment, three measurements will be obtained of both upper extremities: the dorsum of the hand; the midpoint of the volar aspect of the forearm; and the midpoint of the medial aspect of the upper arm. At the initial evaluation, a dermatographic pencil is used to mark the site of each measurement. Once the locations are determined, the exact distance of each location is measured from the wrist. These locations are re-utilized for serial measurements during the trial. The calipers will be calibrated prior to each use. The serial evaluations will be performed by the same operator for each subject, and the operator will be blinded to treatment status and to prior measurement values at the time of each assessment. Each reported skin thickness value represents the arithmetic sum of the three measurements/limb at that assessment. The change in the ratio of ipsilateral:contralateral skin thickness will be analyzed as a secondary endpoint.

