9. STUDY CALENDAR

	Pre-Study	Intervention	Intervention follow-up	Post-op Wk 1 ^c	Post-op Wk 24 ^d	Post-op Wk 36 optional ^d	Post-op Wk 48 ^d	Off Study ^b
Axillary Lymphadenectomy alone, Axillary Lymphadenectomy with STR OR Axillary Lymphadenectomy + LYMPHA^a		X						
Informed consent	X							
Demographics	X							
Medical history	X							
Physical exam	X		X	X	X	X	X	
Vital signs ^f	X	X	X	X	X	X	X	
Height	X		X	X	X	X	X	
Weight	X		X	X	X	X	X	
LYMQOL Patient questionnaire	X					X	X	
Limb volume	X						X	X
Skin Thickness Measurements	X					X	X	
Bioimpedance Spectroscopy (LDex)	X					X	X	
ICG Lymphography		X				X	X	
Adverse event evaluation		X						X

a: Investigation: LYMPHA procedure
b: Off-study evaluation.
c: +/- 1 week
d: +/- 4 weeks
e: demographics refers to first name, last name, MRN, DOB
f: vital signs include BP and HR, with RR and temperature as optional vital signs

A Randomized Clinical Trial of the LYMPHA procedure for the Prevention of Lymphedema after Axillary Lymphadenectomy

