10. MEASUREMENTS

10.1 Primary outcome measure: Incidence of lymphedema

The primary endpoint in this study is a binary outcome variable defined as the presence of lymphedema at Month 12 (“Yes”/”No”), based on the fulfilment of at least one of the following three criteria: (1) More than 10% increase in the relative excess volume of the affected limb; (2) More than 50% time delay of ICG migration from the injection points to the axilla of the affected upper limb in comparison with the contralateral healthy upper limb; or (3) Aggravation of one or more stages in Yamamoto’s classification of the dermal back flow and morphology of the lymphatic collectors.

The efficacy of the LYMPHA procedure will be determined by comparison between the LYMPHA group (Group C) and lymphadenectomy group (Group A).

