12.2 Summary of analyses

Preop visit: After obtaining written consent, medical history, current medications, and allergies will be reviewed, height/weight/VS, physical exam by PI will be conducted, limb measurements performed (volume, BIS, skin thickness), ICG lymphography, and LYMPQOL survey completed.

T1 (1 week following surgery): physical exam, VS, height, weight, photos, symptoms/AE review.

T2 (6 months following surgery): physical exam, VS, height, weight, photos, symptoms/AE review.

T3 (Optional 9 months following surgery): physical exam, measurements (volume, BIS, skin thickness), ICG lymphography, LYMPQOL survey, VS, height, weight, photos, symptoms/AE review.

T4 (12 months following surgery): physical exam, measurements (volume, BIS, skin thickness), ICG lymphography, LYMPQOL survey, VS, height, weight, photos, symptoms/AE review.

Primary endpoint (rate of lymphedema based on volume analysis and ICG analysis) and secondary endpoints (BIS, skin thickness, ICG lymphography and LYMPQOL survey) will be evaluated at final analysis.

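### Section 12.4.2 credits the optional mixed logistic model with using every subject's data, which the visit schedule does not allow, and makes covariate adjustment depend on a baseline significance test

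*Protocol*

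**What the plan says.** Section 10.1 defines the primary endpoint as "a binary outcome variable defined as the presence of lymphedema at Month 12", met by any one of three criteria that rest on limb volume or ICG lymphography. Section 12.4.2 tests it with Fisher's exact test and then adds two things.

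- **Mixed model.** Depending on attrition, a mixed-effects logistic model may also be used. It is said to handle missing data automatically and to be unbiased under missing at random, and then: "This allows the use of all available data from all subjects, thereby minimizing the effects of loss to follow-up".
- **Adjustment.** A logistic regression with covariates is run on a condition: "If treatment arms differ significantly at baseline in demographics (for e.g. age", and so on.

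The schedule is in Section 12.2 (Summary of analyses). The Week 1 visit takes neither volume nor ICG. Nor does Month 6: "T2 (6 months following surgery): physical exam, VS, height, weight, photos, symptoms/AE review". Both are taken at "T3 (Optional 9 months following surgery") and at Month 12. The Section 9 calendar has the same label, "Post-op Wk 36 optional". Section 4, item 2, gives the change formula for criterion 1 at one time only: "excess volume will be determined at month 12".

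A calendar footnote says "demographics refers to first name, last name, MRN, DOB". Section 12.4.1 promises that missing data will be reported and their impact analysed.

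**The concern.** A mixed model softens loss to follow-up when the same outcome is measured repeatedly, so that a patient's earlier values inform the missing one. That fits the continuous secondary outcomes in Section 12.5.2, for which baseline is itself a measurement of the outcome. It fits the primary endpoint poorly: there is one required post-operative status, and baseline status hardly varies because existing lymphedema is excluded (Section 3.2.2).

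The model would be used when attrition is high, which is when a reader looks for reassurance. The result could be taken as corrected for dropout when it merely repeats the complete-case result.

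The adjustment rule is a separate weakness in the same paragraph. In a randomised trial a significant baseline difference is chance, so chance decides whether an adjusted estimate exists. The covariate is picked because it is imbalanced, not because it predicts lymphedema.

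**Working it through.** The plan gives no attrition rate and no figure of its own on this point, so there is nothing to reproduce first. Attrition and observed counts below are assumptions. From the documents: 30 per arm in the new phase (Section 2.4), risks of 30% in Group A and 4% in Group C (12.6.2), 10.3% with LYMPHA after dissection and radiation (2.2), and 5% significance (12.1). All p-values are two-sided Fisher.

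**1. Who contributes to the mixed model.**

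| Attended Month 9 | Attended Month 12 | Contributes a post-operative status |
|---|---|---|
| yes or no | yes | yes |
| yes | no | yes, at Month 9 only |
| no | no | no |

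Suppose 3 of 30 per arm miss Month 12, so 6 across A and C, and a share q of them attended Month 9 independently. The expected number recovered is 6q, and the chance that all six are recovered is q^6.

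| q | 6q | q^6 |
|---|---|---|
| 0.3 | 1.8 | 0.1% |
| 0.5 | 3.0 | 1.6% |
| 0.8 | 4.8 | 26% |

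**2. The limiting case with no Month 9 data.** Take 9/27 in A against 1/27 in C (p = 0.011). The complete-case log-likelihood is 9 ln(9/27) + 18 ln(18/27) + 1 ln(1/27) + 26 ln(26/27) = -21.463. A random-intercept logistic model fitted by 101-point Gauss-Hermite quadrature gives this same maximum, and the same fitted risks of 9/27 and 1/27, with the random-effect SD fixed at 0, 1, 2 or 3. With one observation per patient that SD is not identified, and the model returns the complete-case result.

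**3. What a tipping-point table would show.** Fill each arm back to 30 with every possible number of events among the missing. For 9/27 against 1/27 there are 4 × 4 = 16 cells:

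| Added A events | C+0 | C+1 | C+2 | C+3 |
|---|---|---|---|---|
| 0 | 0.012 | 0.042 | 0.104 | 0.209 |
| 1 | 0.006 | 0.021 | 0.057 | 0.125 |
| 2 | 0.003 | 0.010 | 0.030 | 0.072 |
| 3 | 0.001 | 0.005 | 0.015 | 0.039 |

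Five cells exceed 0.05, and all need at least two added C events. The cells are not equally likely. Let added A events be Bin(m, 0.30) and added C events Bin(m, pC), with m missing per arm. The total probability of the cells with p > 0.05 is then:

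| Missing per arm | Observed | Cells with p > 0.05 | pC = 4% | pC = 10.3% | pC = 30% |
|---|---|---|---|---|---|
| 1 | 9/29 vs 1/29 (p = 0.012) | 0 of 4 | 0% | 0% | 0% |
| 2 | 9/28 vs 1/28 (p = 0.012) | 2 of 9 | 0.1% | 1.0% | 8.2% |
| 3 | 9/27 vs 1/27 (p = 0.011) | 5 of 16 | 0.4% | 2.3% | 17.4% |
| 6 | 8/24 vs 1/24 (p = 0.023) | 27 of 49 | 3.9% | 13.5% | 51.9% |

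**4. The baseline trigger.** With no true imbalance it fires in 5% of trials for one test, and in 1 - 0.95² = 9.75% for two independent tests. A simulation (30 per arm, 30% risk in both arms, one covariate with an assumed odds ratio of 2.5 per SD, 6,000 runs) gave a trigger rate of 4.7%. Type I error was 2.5% for the two-step rule, 2.4% for Fisher alone and 5.5% for ordinary logistic regression always adjusted (likelihood-ratio test).

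**5. Sparse events.** The chance of no Group C event among 30 is 0.96^30 = 29% at 4% risk and 0.897^30 = 3.8% at 10.3%. With no event in an arm, ordinary logistic regression has no finite estimate of the treatment effect.

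**The case against.** The disputed model is optional and conditional, and Fisher's exact test is the stated analysis. That the model uses the available data is literally true; only the extension to every subject, and the conclusion drawn from it, go too far. Section 12.4.1 already commits to analysing the impact of missing data, and the method could sit in a SAP not seen here. All of this stands and limits the point to a correction of wording and method.

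Four stronger readings are tempting, and the documents do not support them.

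- **That the model is biased and should be dropped.** If missingness depends only on arm and modelled covariates, a complete-case logistic likelihood is valid, so the missing-at-random sentence is not false. The model is also the only stated primary-endpoint analysis that could use a Month 9 status. Criteria 2 and 3 can be assessed at that visit. Excess volume is computed at each measurement, so criterion 1 lacks only a Month 9 version of its change formula. The identity in step 2 is a limiting case; nothing says that nobody will attend.
- **That dropout makes the primary result fragile.** A count such as 27 of 49 suggests this, but those cells carry 3.9% probability at the planned LYMPHA risk. They pass one half only if missing Group C patients carry the full control risk.
- **That the trigger inflates type I error.** The simulation shows 2.5% against 2.4%.
- **That adjustment could only ever be for age.** The calendar footnote points that way, but 12.4.2 gives age as an example and leaves the covariates open.

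One caution on sources: in the calendar as extracted, limb volume is not marked at Week 36. The table may have shifted in extraction, so the Month 9 volume is taken from Section 12.2 and nothing is built on the difference.

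**Conclusion.** The point holds as a correction to Section 12.4.2. The statement that the mixed model uses data from every subject and so minimises the effects of loss to follow-up describes a property this design does not have. Recovery is limited to patients who miss Month 12 but attended an optional visit: 1.8 to 4.8 of 6 under the assumed attrition and attendance of 30% to 80%, and none if no such patient attended.

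The baseline trigger is a poor rule. It fires by chance in 5% of trials per test and ignores prognostic value, but its shown cost is a data-dependent and badly chosen supportive analysis, not a false-positive problem. The primary test is unaffected. The visit schedule and the wording of 12.4.2 are firm. The sizes rest on assumed attrition, Month 9 attendance, observed counts and risks among missing patients.

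**What to change.** Three changes in Section 12.4.2, with Fisher's exact test kept as the primary analysis and the optional mixed model retained.

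1. Replace the sentence on using all subjects' data with, for example: *The optional mixed model uses only patients with a lymphedema status at Month 9 or Month 12; it does not recover patients with neither.*
2. To carry out the commitment in 12.4.1, add: *The impact of missing Month 12 status will be examined by a tipping-point table over the possible numbers of events among missing patients in each arm, reported with the plausibility of the cells under stated risks and not as a count of cells.*
3. Replace the baseline-significance condition with: *One supportive adjusted analysis will be run regardless of baseline tests, by Firth-penalised logistic regression with age as the covariate.* Penalisation keeps the estimate finite if an arm has no events.

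The cost is wording and slightly more analysis work. Age is already available from date of birth, so no new visits, data or CRF fields are needed.
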